4. OBJECTIVE AND LONG-TERM VISION OF THE MMC

The objective of the MMC is to launch a new metabolic disease management model based on the Internet health information platform. Moreover, the MMC helps improve adherence to and the effectiveness of treatment for patients, thus benefitting both patients and doctors. The proprietary electronic medical database in the MMC will make dynamic big-data analysis in diabetes epidemiology, prevention, diagnosis, and treatment very efficient and effective. Furthermore, this nationwide standardized care system also forms a collaborative research network for prospective interventional studies on treatment and prevention. Therefore, in the long run, the MMC will offer large amounts of data and evidence from hospital-based care to achieve long-term optimal health outcomes, enabling a replicable standard care model across the entire country that can form the base for future healthcare policy improvement.

Objective

1. To establish a multi-center nationwide prospective database of diabetes patients in MMCs, including clinical data, biological samples library so as to explore the epidemiology, genetics, new biomarkers, risk factors, and prognostic methods related to diabetes and its complications, as well as other metabolic diseases.

2. To collect cross-sectional data from patients seen and treated at each MMC centers so as to evaluate: the current status of care of patients with diabetes and its related complications, as well as other risk factors treatment strategies at these centers. Patients' costs and quality of life (QoL) will also be evaluated.

3. To collect the prospective data of patients treated at each MMC centers in order to evaluate the strategies for the achievement of treatment goals, changes in management, control of risk factors, incidence and progression of all-diabetes related clinical endpoints (including mortality), behavioral changes, psychological well-being as well as costs and QoL.

5. Study Population:

All the patients who are seen and treated at each MMC centers, and meet the Inclusion/Exclusion Criteria will be included in this study.

Main Inclusion Criteria:

• Age \geq 18 years old

• Diagnosis of diabetes according to the diagnostic criteria for diabetes at the time of enrollment.

- Gender: males and females
- Fully understand the study and provide written informed consent

• With satisfactory compliance

Main Exclusion Criteria:

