6.3.2 Medical History

The information collected in the section of medical history is shown in Table 1. The diagnosis of diabetes is confirmed if the participant has a self-reported history of diagnosed diabetes by professionals, and/or fasting blood glucose (FBG) \geq 7.0 mmol/L, and/or 2h postprandial blood glucose (PBG) \geq 11.1 mmol/L according to the 1999 World Health Organization (WHO) diagnostic criteria [11]. Since 2021, glycated hemoglobin (HbA1c) \geq 6.5% was added into the diagnostic criteria for diabetes in accordance with 2020 guidelines for the prevention and treatment of type 2 diabetes in China. The duration of diabetes is determined by the following criterion: 1) the accurate time diagnosed with diabetes patients provided; 2) Newly diagnosed with diabetes (patients reported never diagnosed with diabetes before), the duration of diabetes is "0"; 3) if the information of whether diagnosed with diabetes, the information of diabetic duration is missing.

1) Types of diabetes

At each MMC, a qualified medical practitioner was responsible for determining the specific type of diabetes. Participants with type 1 diabetes (T1DM), gestational diabetes mellitus (GDM), and other specific forms of diabetes were excluded from the study. In cases where the type of diabetes was unclear, T1DM was diagnosed based on the presence of glutamic acid decarboxylase antibodies (GADA) and low C-peptide concentrations (<0.8 ng/mL). A comprehensive review of medical records and laboratory tests, including thyroid and adrenal hormone profiles, and other

11 / 35

relevant parameters, was conducted to exclude rare or unusual cases of diabetes. For a more detailed account of these diagnostic procedures, please refer to our previously published article [12].

2) Other metabolic related disease

(1) Hypertension: Ever diagnosed by physicians; or when measuring the clinic blood pressure on three different days without the use of antihypertensive medications, systolic blood pressure (SBP) is \geq 140mmHg and/or diastolic blood pressure (DBP) is \geq 90mmHg. If a patient has a history of hypertension and is currently taking antihypertensive medications, even if their blood pressure is lower than 140/90mmHg, they should still be diagnosed with hypertension.

(2) Hyperlipidemia: Ever diagnosed by physicians; or when enrolled in MMC, laboratory tests showed LDL-C \geq 3.4 mmol/L (130 mg/dl) and / or TG \geq 1.7 mmol/L (150 mg/dl).

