6.4 Follow-up Questionnaires

Planned follow-up surveys will be conducted every 3 months from baseline. The follow-up questionnaires are specified in standard operating procedures (SOPs) and presented in Table 1 (taking one year as an example). Symptoms and lifestyle factors will be collected at one-year interval. For each follow-up visit, patients' actual medication use and adverse events (with pre-defined categories of diseases) needs to be recorded repeatedly and registered in the electronic medical record system. Adverse events refer to any adverse medical events that occur during the patient's visit, which could be any unwell sign, symptom, disease, or laboratory abnormality. The registered adverse events mainly include cardio-cerebrovascular events, severe hypoglycemia, cancer, hospitalization, laser coagulation treatment for diabetic

retinopathy (DR), and other adverse events that local doctors judge necessary to record. Details are formulated in the corresponding chapter ('Assessing and Recording of Adverse Events').

For patients who have been lost to facility-based follow-up, the staff will be proposed to make a telephone follow-up. If the call gets through and death is learned, death registration (e.g., date, causes of death) will be completed by the staff. Hospital records and death certificates will be supplemented if available.

7. Physical Measurements

Height, weight and blood pressure are recorded at each visit. Head circumference is obtained at the baseline visit without repeated measurements later. Circumferences of neck, waist and hip, visceral fat area (VFA) and subcutaneous fat area (SFA) are recorded once a year. VFA and SFA measurements is required for regional MMC, and optional for county and community MMC (Table 2).

	Arranged follow-up visits					
Variables	Baseline	seline Month 3*		Month 6 Month 9*		
Physical measurements						
Height and weight						
Blood pressure and heart rate						
Head circumference						
Neck, waist and hip						
circumference						
VFA and SFA						
Laboratory tests						
Blood and urine routine						
Biochemical tests						
HbA1c						

Table 2. The required items for physical measurements and clinical examination in different levels of MMC (according to follow-up visits arranged within each year)

FBG			
PBG			
Fasting serum			
insulin/C-peptide			
Postprandial insulin/C-peptide	$\Box \bigcirc$		
UACR			
Islet autoantibodies			
Thyroid hormone			
Examination of			
diabetes-related			
complications			

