8.3 Clinical Examination at Follow-up Visits

According to the standard protocol, two to four follow-up visits every year are arranged for enrolled patients, with the same follow-up frequency formulated for regional, county, or community MMCs. The actual number of visits may be changed depending on patients' condition and compliance. The flow chart for clinical examination at each visit within one-year period are listed in Table 2. The clinical examination in the follow-up stage beyond one year are also performed with reference to Table 2.

Urinary albumin-to-creatinine ratio (UACR) will be collected every six months to define the status of proteinuria. Fundus photography and screening for diabetic neuropathy will be performed annually. The patients with moderate DR or worse will be referred to the ophthalmology department for further examination and treatment. Carotid ultrasonography, baPWV and ABI will be evaluated at least 3 times during the 5-year follow-up period (baseline, year 2 or year 3, and year 5). ECG and echocardiogram will be arranged at least twice within 5 years (baseline and year 5). The screening frequency of diabetes related complications may be adjusted if necessary.

9. Clinical Outcome Measures

9.1 Primary outcome measures: The primary outcomes include incidence of all diabetes-related clinical endpoints:

1) Mortality

- (1) Total mortality;
- (2) Cardiovascular mortality: includes fatal myocardial infarction (MI), death due

to stroke, fatal congestive heart failure, unexpected death presumed to be due to ischemic cardiovascular disease, death due to documented arrhythmia, and death due to other cardiovascular diseases;

- (3) Fatal renal failure
- 2) The Macrovascular morbidity
 - (1) Coronary heart disease
 - a) non-fatal MI or ischaemic heart disease
 - b) Coronary revascularization or coronary artery bypass surgery
 - c) Percutaneous transluminal coronary angioplasty (PTCA)
 - (2) Carotid angioplasty with or without stent; Carotid endarterectomy
 - (3) Peripheral vascular disease
 - a) Peripheral angioplasty with or without stent;
 - b) Peripheral vascular surgery (including aortic aneurysm repair);
 - c) Peripheral circulatory disorders;
 - d) Peripheral vascular disease;
 - e) Limb amputation due to vascular disease;
 - f) Gangrene.
 - (4) Stroke
 - a) Ischaemic stroke (a nonvascular etiology must be absent);
 - b) Intracerebral haemorrhage;
 - c) Subarachnoid haemorrhage;

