 - d) Other and unspecified intracranial haemorrhage;
 - e) Stroke of unknown type etiology.
- 3) Non-fatal congestive heart failure
- 4) The Microvascular morbidity
 - (1) Diabetic kidney disease (DKD):
 - a) Chronic kidney disease: Estimated glomerular filtration rate (eGFR) <60 ml/min/1.73m² (as estimated by the EPI equation, eGFR=141 × min(Scr/κ, 1)^α × max(Scr/κ, 1)^{-1.209} × 0.993^{Age} × 1.018 [if female] _ 1.159

[if black], where Scr is serum creatinine in mg/dl, κ is 0.7 for females and 0.9 for males, α is -0.329 for females and -0.411 for males, min represents the minimum of Scr/ κ or 1, and max represents the maximum of Scr/ κ or 1).

- b) End-stage renal disease: Estimated glomerular filtration rate (eGFR) <15 ml/min/1.73m², or need dialysis, or need renal transplant
- c) Development of microalbuminuria (urinary albumin/creatinine ratio
 [UACR] ≥30 and < 300mg albumin per gram creatinine, or UACR ≥
 3.39 and < 33.9 mg/mmol in a random sample)
- d) Development of macroalbuminuria (urinary albumin/creatinine ratio
 [UACR] ≥ 300mg albumin per gram creatinine, or UACR ≥ 33.9
 mg/mmol in a random sample)
- (2) Diabetic retinopathy (DR):
 - a) If both eyes' images were evaluable, the more severe DR grade between the two was adopted.
 - b) If only one eye's image was gradable, the DR grading relied solely on that eye.
 - c) If no gradable image was available for either eye, the patient was classified as ungradable.
 - d) In cases of discrepancy between the on-site and qualified AI result, the more severe DR grade was selected.
 - e) Any occurrence of the following adverse events was classified as an incidence of DR: undergoing laser treatment or therapy with anti-vascular endothelial growth factor (VEGF) inhibitors, experiencing vitreous/preretinal hemorrhage, clinically significant macular edema (CSME), undergoing vitrectomy, or developing diabetes-related blindness.
- 5) Neuropathy
- 6) Cancer:

The occurrence of any of the cancers include prostate, breast, lung/bronchus, endometrial, colon, gastric, leukemia, lymphoma, pancreas, kidney/renal pelvis, rectal, and melanoma;

- Major infections: include chronic and acute infections, pulmonary and non-pulmonary;
- 8) Hospitalization for any of the above reasons.
- 9.2 Secondary Outcome Measures:
- 1) Glycated haemoglobin (HbA1c, %)
- 2) Fasting and postprandial glucose concentrations (mmol/L)

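### Section 9.1 defines albuminuria and eGFR <60 by threshold alone, so a stable patient near a cut-off can count as an incident primary event on one transient result

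*Protocol*

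**What the plan says.** Section 9.1 names incidence of all diabetes-related clinical endpoints as the primary outcome, and objective 3 in section 4 asks for incidence and progression. Under microvascular morbidity, diabetic kidney disease has four items:

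- "Chronic kidney disease: Estimated glomerular filtration rate (eGFR) <60" ml/min/1.73 m², with the estimating equation written out;
- "End-stage renal disease: Estimated glomerular filtration rate (eGFR) <15", or need for dialysis or transplant;
- "Development of microalbuminuria (urinary albumin/creatinine ratio" of at least 30 and below 300 mg/g, in a random sample);
- "Development of macroalbuminuria (urinary albumin/creatinine ratio" of at least 300 mg/g, in a random sample).

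None carries a duration, repeat or confirmation term, and I found none elsewhere in the protocol. The automatic checks in section 10 ask staff to review data entries. They do not confirm endpoints.

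On timing, section 8.3 states: "Urinary albumin-to-creatinine ratio (UACR) will be collected every six months to define the status of proteinuria". It also plans two to four visits a year, lets the actual number depend on the patient's condition and compliance, and allows complication screening to be adjusted. Section 6.4 states: "Planned follow-up surveys will be conducted every 3 months from baseline".

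**The concern.** UACR and eGFR vary from one sample to the next within a person. If any single result beyond the cut-off counts as the event, the rule gives each patient as many chances of a chance crossing as there are tests. Patients whose kidney function has not changed can then enter the primary incidence count, and more easily the more often they attend. Differences in attendance between patients, centres or regions could then show up as differences in incidence. The label chronic for eGFR <60 also claims a duration that the definition does not require.

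Dialysis and transplant are not threshold results and are unaffected. A chance crossing of eGFR 15 matters only for patients already close to 15, so that limb has little practical weight.

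**Working it through.** **Figures in the plan.** The protocol gives no sample size, event count or expected incidence, so there is no design figure to reproduce. Its UACR cut-offs agree across units: 3.39/30 = 33.9/300 = 0.113.

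**Inputs.** From the protocol: cut-offs 30 mg/g and 60 ml/min/1.73 m² (9.1) and six-monthly UACR (8.3). Assumed: within-person CV of 30% to 60% for UACR and 5% to 8% for eGFR; 4, 6 or 10 UACR tests (2, 3 or 5 years at two a year). Section 8.3 mentions a 5-year period, but only for other examinations; no horizon is stated for UACR. Five eGFR values are assumed, because the follow-up columns of Table 2 are not readable in the text at hand.

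**Formulas, for a patient whose true value does not change**

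- UACR, log-normal error: σ = √ln(1+CV²), p = 1 − Φ(ln(30/true)/σ).
- eGFR, normal error: p = Φ((60 − true)/(CV × true)).
- At least one crossing in n tests: 1 − (1 − p)ⁿ.
- Two consecutive crossings: let a = no pair yet and last test not crossed, b = no pair yet and last test crossed. At each test the pair probability grows by b·p, then a becomes (a+b)(1−p) and b becomes the old a times p.

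Example, UACR 15 mg/g with CV 60%: σ = √ln 1.36 = 0.5545; ln 2/0.5545 = 1.25; p = 0.106; 1 − 0.894¹⁰ = 67%.

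| True UACR (mg/g) | CV | p | ≥1 in 4 | ≥1 in 6 | ≥1 in 10 | Pair in 4 | Pair in 6 | Pair in 10 |
|---|---|---|---|---|---|---|---|---|
| 5 | 60% | 0.0006 | 0.2% | 0.4% | 0.6% | ~0 | ~0 | ~0 |
| 10 | 30% | 0.0001 | 0.04% | 0.05% | 0.1% | ~0 | ~0 | ~0 |
| 10 | 60% | 0.024 | 9% | 13% | 21% | 0.2% | 0.3% | 0.5% |
| 15 | 30% | 0.009 | 3.6% | 5.3% | 8.7% | 0.02% | 0.04% | 0.07% |
| 15 | 60% | 0.106 | 36% | 49% | 67% | 3.1% | 5.1% | 8.9% |
| 25 | 30% | 0.267 | 71% | 85% | 96% | 18% | 27% | 43% |

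If errors at adjacent tests correlate at 0.3 on the log scale (simulation of 1,000,000 patients, 15 mg/g, 10 tests, CV 30% to 60%), the figures are 8% to 62% for a single result and 0.4% to 16% for a pair. The gain from confirmation shrinks but remains.

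| True eGFR | CV | p | ≥1 in 5 | Pair in 5 |
|---|---|---|---|---|
| 65 | 5% | 0.062 | 27% | 1.5% |
| 65 | 8% | 0.168 | 60% | 9.8% |
| 70 | 8% | 0.037 | 17% | 0.5% |
| 80 | 8% | 0.0009 | 0.4% | ~0 |

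**What confirmation costs.** Take a true, persistent UACR of 45 mg/g, with onset spread evenly over 10 tests (p = 0.916 at CV 30%, 0.768 at CV 60%). Averaging over 1 to 10 remaining tests, with attended tests binomial:

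| Attendance | Single result | Two consecutive |
|---|---|---|
| 100% | 97–99% | 80–87% |
| 80% | 94–96% | 73–82% |
| 60% | 88–92% | 62–72% |

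With full attendance and at least two tests left after onset, confirmed detection is 89–97%. For a true eGFR of 55 with five values it is 97–99% single, 71–78% confirmed, and 89–97% with at least two values left.

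**Dependence on the number of tests** (15 mg/g, CV 60%, 10 against 4 tests): single 67% − 36% = 31 points, ratio 1.9; pair 8.9% − 3.1% = 6 points, ratio 2.9.

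**The case against.** **The SAP, the SOPs or the management guideline may hold a confirmation rule.** They are not shown, and derivation rules often sit there. The words about a random sample can mean spot urine rather than a statement that one specimen suffices, and serial UACR fits either rule. This stands as a caution: a reader might infer that the protocol expressly accepts one result, and it does not say so. But section 9.1 does more than leave the matter open. It fixes these endpoints in detail, down to the constants of the eGFR equation, and as written any qualifying result meets them.

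**The protocol does not contradict itself here.** A reader might point to section 6.3.2, where measured hypertension requires readings taken "when measuring the clinic blood pressure on three different days without the use of antihypertensive medications", and infer an inconsistency. That contrast is weak. The same section classifies hyperlipidemia and diabetes on cut-offs with no repeat stated, and the hypertension rule is a history definition rather than an outcome.

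**The size is assumed.** This stands in full. CVs, error model and test counts do not come from the document, and the width of the ranges shows a mechanism, not a magnitude.

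**Confirmation is a trade-off.** This stands in part. Sensitivity falls, and the relative dependence on attendance rises even though the absolute gap shrinks. It argues against replacing the single-result count, not against reporting a confirmed count beside it. Because results are recorded as values, both can be derived from data already collected. That also limits the harm, but a choice between them made after seeing the data would be open to question.

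**Conclusion.** The point holds in a limited form. Section 9.1 sets microalbuminuria, macroalbuminuria and eGFR <60, and with little practical weight the eGFR <15 limb of end-stage renal disease, by threshold alone. A stable patient near a cut-off can be counted as an incident primary event on one transient result, more often with more tests. Microalbuminuria and eGFR <60 are the main concern; no figures were worked for the other two.

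That the wording lacks a repeat term is certain, and the mechanism follows by arithmetic. The percentages rest on stable true values, the assumed CVs, independent errors (except where correlation is stated) and assumed test counts. A reader might infer that the cohort's reported kidney incidence will be inflated by a known or large amount. The document does not support that: it gives no distribution of true UACR or eGFR, and patients far from a cut-off contribute almost nothing. No sample size or other design figure is affected.

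**What to change.** Analysis wording only, with no extra visits or tests.

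1. Pre-specify a confirmed version of the albuminuria and eGFR-based endpoints: a qualifying result counts when the next available result at least 3 months later also qualifies, and the event is dated at the first result. Three months is the shortest spacing in section 6.4; consecutive six-monthly UACR tests meet it.
2. For microalbuminuria, any later UACR of 30 mg/g or more confirms, including 300 or more. The paired figures above assume that the next result does the confirming. After a qualifying eGFR, dialysis, transplant or renal death confirms without a second value.
3. Report confirmed and single-result incidence side by side, and describe eGFR <60 as chronic kidney disease only for the confirmed version.
4. For event-free patients, end at-risk time for the confirmed endpoint at the last result that has a further result at least 3 months after it.
5. Report the number of tests per patient and the number of unconfirmed last results.

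The cost is the loss of some true late-onset or remitting cases from the confirmed count. Confirmation does not remove dependence on attendance, and it does not rescue patients very close to a cut-off: at a true 25 mg/g and CV 30%, 43% still show a consecutive pair in 10 tests. These limits are the reason for keeping both counts.

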8.2 Baseline Examination of Diabetes-related Complications

8.2.1 Fundus Photography

Fundus examination is performed for all diabetic patients by an experienced and trained technician. One color macula-centered fundus image will be acquired from each eye. Fundus images are taken without pupil dilation and with a 45-degree field of view. The worse diabetic retinopathy (DR) classification of the two eyes will be chosen as the final patient-level DR grade. The status of DR is defined as "yes" if mild non-proliferative DR (NPDR) or above is present. We describe DR grade by

following definitions: referable DR (moderate NPDR or above); vision-threatening DR (VTDR, severe NPDR or above and/or clinically significant macular edema [CSME])[12]. The definition for VTDR may be modulated and specified in certain studies.

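### The retinopathy endpoint takes the more severe of the on-site and AI grades where both exist, without requiring the same grading basis at a patient's baseline and follow-up visits

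*Protocol*

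**What the plan says.** Section 9.1 opens with "The primary outcomes include incidence of all diabetes-related clinical endpoints", and DR is item 4)(2). Two maxima are built into its grade. Rule a) works across eyes: "If both eyes' images were evaluable, the more severe DR grade between the two was adopted". Rule d) works across readers: "In cases of discrepancy between the on-site and qualified AI result, the more severe DR grade was selected". Section 8.2.1 sets DR status to yes "if mild non-proliferative DR (NPDR) or above is present", so one step up from normal makes a case. It also describes the image: "Fundus images are taken without pupil dilation and with a 45-degree field of view". Section 8.3 sets the frequency: "Fundus photography and screening for diabetic neuropathy will be performed annually".

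The wording of 8.2.1 describes photography and grading without mentioning an AI result, although one reference it cites is a study of AI-enabled screening. The AI grade enters only in rule d), where the term qualified is not defined. No section says which centres, visits or calendar years have an AI result. None says that baseline and follow-up grades must come from the same source.

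**The concern.** Incidence is a change between two gradings. It is interpretable only if both are made in the same way, or if the difference is known. Rule d) makes the grading method depend on whether a second result exists at that visit. If the second result appears after baseline, follow-up becomes more sensitive and less specific than entry. DR missed at entry and standing errors of the second reader then both surface as new disease.

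Incidence and progression of clinical endpoints are named in Objective 3 (section 4), and section 11 divides patients into seven regions. If AI availability differed by year, centre tier or region, its effect could be taken for a time trend or a regional difference. There is no brake on a wrong mild grade: no adjudication, repeat image or later confirmation is described. Referral starts higher, "The patients with moderate DR or worse will be referred to the ophthalmology department for further examination and treatment", and nothing says that its result can overturn the endpoint grade.

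**Working it through.** The protocol states no reader accuracy, event rate or sample size for this endpoint, so there is no figure to reproduce.

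**Inputs from the protocol.** Rule d); threshold at mild disease; yearly photography. The five-year horizon comes from section 8.3, where it is stated for carotid ultrasonography, baPWV and ABI ("at least 3 times during the 5-year follow-up period"). Five follow-up fundus screens is therefore an assumption.

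**Assumed inputs.** Two readers of equal accuracy: specificity (Sp) 0.95 to 0.995, sensitivity (Se) 0.70 to 0.90. Baseline prevalence 20% or 30%. True incidence 3% a year, so 1 − 0.97^5 = 14.1% over five years. Errors independent between readers and between years unless stated.

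**Step 1: false positives at one screen.** With the more severe of two grades and independent errors, the rate in a DR-free patient is 1 − Sp1 × Sp2. With fully overlapping errors it is the rate of the less specific reader.
- Sp 0.95 each: 1 − 0.95² = 9.75%, against 5% for one reader (simple sum 10%).
- Sp 0.98 each: 1 − 0.98² = 3.96%, against 2% (simple sum 4%).

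So the rate lies between that of the less specific reader and about the sum of both.

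**Step 2: five screens in a patient who stays DR-free.** 1 − (1 − rate)^5, one reader against the rule:
- Sp 0.95: 22.6% against 40.1%.
- Sp 0.98: 9.6% against 18.3%.

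These are upper-end values, because they need errors independent between readers and between years. They are also not the observed incidence, because they leave out sensitivity.

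**Step 3: observed five-year incidence.** Take patients graded negative at baseline. Missed DR is prevalence × (1 − Se); true negatives are (1 − prevalence) × Sp. Each year 3% of the DR-free convert. Existing undetected DR is then flagged with probability Se, and the remaining DR-free with probability 1 − Sp. Observed incidence is everyone flagged in five years divided by the baseline-negative group. For the more severe of two, Se becomes 1 − (1 − Se)² and Sp becomes Sp².

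| Prevalence | Se | Sp | One reader throughout | Rule d) throughout | One reader at baseline, rule d) later |
|---|---|---|---|---|---|
| 20% | 0.90 | 0.95 | 35.0% | 48.7% | 49.9% |
| 20% | 0.90 | 0.98 | 24.0% | 30.0% | 31.6% |
| 20% | 0.90 | 0.99 | 20.1% | 22.5% | 24.2% |
| 30% | 0.70 | 0.99 | 26.7% | 25.0% | 31.0% |
| 20% | 0.80 | 0.995 | 19.6% | 19.0% | 22.1% |
| 30% | 0.90 | 0.995 | 19.4% | 18.7% | 21.7% |

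The true value is 14.1% in every row. Rule d) throughout is above one reader in the first three rows and below it in the last three. The changing basis is highest in all six: 2.2 to 14.9 percentage points above one reader, and 1.2 to 6.0 above rule d) throughout.

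**Step 4: why the changing basis stands out.** Take the second row. One reader at baseline leaves 0.20 × 0.10 = 0.020 missed DR in a baseline-negative group of 0.020 + 0.80 × 0.98 = 0.804, which is 2.5%. Rule d) at baseline leaves 0.20 × 0.01 = 0.002 in 0.002 + 0.80 × 0.9604 = 0.770, which is 0.26%. With a changing basis the 2.5% is carried forward and then found by the more sensitive reading.

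Errors that persist in the same eye behave alike. With a constant basis they are removed at entry. If AI errors persist fully and are independent of on-site errors, a changing basis counts 1 − Sp of the truly DR-free as incident at the first follow-up: 2% at Sp 0.98, 5% at 0.95.

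The direction against one reader needs no accuracy figure. In the same baseline-negative patients, the worse of two grades flags everyone whom the on-site grade flags, and possibly others.

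**The case against.** A reader might infer from rule d) that the protocol inflates DR incidence outright, to about double. The document does not support that. The doubling applies to false positives in DR-free patients, under full independence. In observed incidence, the first three rows give ratios of 48.7/35.0 = 1.39, 30.0/24.0 = 1.25 and 22.5/20.1 = 1.12. In the last three rows the rule lowers observed incidence and brings it nearer the truth, because fewer cases missed at entry are counted later. With one undilated image per eye, missed disease is plausible. Rule d) used consistently is a trade of specificity for sensitivity, and moving to one reader as the main definition is not clearly better. This part of the objection stands.

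A reader might also infer that patients are in fact read once at entry and twice later. No section says so. The protocol is silent on AI coverage, and operating procedures or an analysis plan not shown here may settle it. The opposite order, two results at baseline and one later, would push the estimate the other way.

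What survives is narrower. The protocol itself fixes the endpoint grade by a rule that varies with the availability of a second result, and it does not hold that basis constant within a patient.

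**Conclusion.** The point holds as a gap in the endpoint definition. Per screen, rule d) puts false positives between the rate of the less specific reader and about the sum of both. Its net effect on incidence against a single reader cannot be signed from the document, because reader accuracy and baseline prevalence are not given.

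Where a patient has one result at baseline and the worse of two later, incident DR is biased upward without any retinal change. Under the assumptions above, the excess over a single-reader basis is 2.2 to 14.9 percentage points in the patients affected. The cohort-wide effect scales with their share, which is unknown: it is nil if AI coverage is complete or absent at all visits. The matter is worth correcting because DR is a primary outcome and the correction is cheap. It is not evidence that the reported incidence will be wrong.

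**What to change.** Add to 9.1, item 4)(2), that for incidence and progression the baseline grade and every follow-up grade of a patient are derived on the same basis, meaning the same source or sources at all visits used. Where an AI result is missing at any of those visits, use the on-site grade at all of that patient's visits. Report incidence under a single-source grade next to the more-severe-of-two grade, so that the influence of the rule is visible. State AI coverage by visit, centre tier and region. Any use of the more severe grade for clinical flagging is left as it is.

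Cost: slightly more derivation work, and some AI information lost in patients with incomplete AI reads. The on-site and AI results must be held as separate fields, which the protocol does not confirm. A constant basis within patients does not make patients or centres comparable with each other. The single-source result helps there, although on-site readers may themselves differ between centres.

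### The event-based rule for incident diabetic retinopathy (DR) in section 9.1 sets no indication, so treatment for non-diabetic eye disease can be counted as a primary DR event

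*Protocol*

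**What the plan says.** Section 9.1 introduces the primary outcomes with "The primary outcomes include incidence of all diabetes-related clinical endpoints". Under microvascular morbidity, the DR item has five rules. Rules a) to d) cover image grading: the worse eye, a single gradable eye, ungradable images, and disagreement between the on-site and AI grades. Rule e) is a separate, event-based route: "Any occurrence of the following adverse events was classified as an incidence of DR". Its list contains "undergoing laser treatment or therapy with anti-vascular endothelial growth factor (VEGF) inhibitors", then vitreous or preretinal hemorrhage and CSME, and ends with "undergoing vitrectomy, or developing diabetes-related blindness".

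Section 6.4 describes how adverse events are registered. The main categories it names include "cancer, hospitalization, laser coagulation treatment for diabetic", continuing after a page break with "retinopathy (DR), and other adverse events that local doctors judge necessary to record". For further detail it points elsewhere: "Details are formulated in the corresponding chapter ('Assessing and Recording of Adverse Events". That chapter is not in the text at hand.

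Section 8.2.1 defines DR on images as mild non-proliferative DR or above. It allows the definition to be adapted later for vision-threatening DR, and states no such allowance for DR of any grade.

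**The concern.** Three components of rule e) are treatments and one is a hemorrhage. All four can arise from eye disease unrelated to diabetes. Only blindness carries an explicit diabetes qualifier. CSME is linked to DR through its use in section 8.2.1. Anti-VEGF therapy is also not limited to the intraocular route.

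A patient without retinopathy who has one of these events for another reason therefore meets the definition of a primary outcome. The direct effect would be to overstate DR incidence. If treatment for other eye disease varies with age or with access to ophthalmology, the false events would not be evenly spread. Comparisons by age, by centre, or across the seven regions of section 11 could then be distorted, as could risk-factor associations. The protocol gives no data to show whether or how far this happens.

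**Working it through.** The protocol states no event rate, sample size or power for DR, so there is no figure to reproduce. The check is a reading of the text, component by component.

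| Component of rule e), section 9.1 | Tied to diabetic eye disease in 9.1? | Treatment in section 6.4 |
|---|---|---|
| Laser | No | Named, and specified as laser coagulation for DR |
| Anti-VEGF therapy | No; route not stated | Not named; can enter through the local-judgement category |
| Vitreous/preretinal hemorrhage | No | Not named; same route |
| CSME | Not in words, but used for vision-threatening DR in 8.2.1 | Not named |
| Vitrectomy | No | Not named; same route |
| Blindness | Yes | Not named |

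**Step 1: can a clean image override rule e)?** No. Rules a) to d) only settle which image grade to use. Rule e) opens with any occurrence and works independently of the grade.

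**Step 2: does the protocol attribute cause elsewhere?** Yes. In the same section, limb amputation counts when it is due to vascular disease, and ischaemic stroke requires that a nonvascular cause be absent. Section 6.4 ties laser to DR. The lack of attribution in rule e) is therefore not a general style of the document.

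**Step 3: could other recorded data supply the indication?** Not on what is shown. Section 6.4 records medication use at each visit, but the fields that section 6.3.3 lists for baseline medication are usage, dosage and dates, not indication. Section 6.4 lists no indication field for anti-VEGF therapy or vitrectomy.

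**Step 4: size, on assumed values only.** Let p be the true cumulative DR incidence, and f the share of DR-free patients who have a listed event for another reason. The share of counted DR events that are false is

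f(1 − p) / [p + f(1 − p)].

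Neither p nor f is in the protocol. With p assumed at 10% to 20% and f at 0.2% to 2%:

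- p = 20%, f = 0.2%: 0.0016 / 0.2016 = 0.8%
- p = 10%, f = 0.2%: 0.0018 / 0.1018 = 1.8%
- p = 20%, f = 2%: 0.016 / 0.216 = 7.4%
- p = 10%, f = 2%: 0.018 / 0.118 = 15.3%

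The spread comes entirely from the assumptions. It shows that the effect could be negligible or noticeable; it is not an estimate for this cohort.

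**The case against.** The strongest reply is that context supplies the missing qualifier. Rule e) stands under a DR heading, within microvascular morbidity, within diabetes-related endpoints. It classifies registered adverse events, and the registered laser category is already laser for DR. Attribution rules may also sit in the adverse-event chapter or in the standard operating procedures. And a sensitive rule is defensible when screening uses one undilated 45-degree image per eye and some images are ungradable.

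Part of this stands:

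- **Laser.** A reader might infer that 9.1 counts every kind of laser, such as laser for glaucoma or after cataract surgery. The documents do not establish that. The named category in 6.4 is tied to DR, although the list is open and laser for other reasons could enter through local judgement. What the text supports is that the wording of 9.1 and 6.4 differs and should be aligned.
- **Cancer drugs.** A reader might also infer that systemic anti-VEGF therapy for cancer becomes a DR event. The wording does not name a route, but in a list of eye treatments and eye complications that reading is strained. Such a drug would more naturally be recorded as medication or with the cancer event.
- **Actual practice.** The documents show what the definition permits, not what sites record. The chapter not at hand may restrict entries.

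The rest does not remove the point. The headings state a general intent and do not attribute individual events; if they did, the qualifier on blindness would be redundant. Section 6.4 does not restrict anti-VEGF therapy, vitrectomy or hemorrhage to diabetic causes. Sensitivity can be kept without counting an event whose documented cause is not diabetic.

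**Conclusion.** The point holds as a fault in a stated endpoint definition. Followed as written, rule e) lets anti-VEGF therapy, vitrectomy or vitreous/preretinal hemorrhage from non-diabetic eye disease count as a primary DR event, even with clean images. For laser, the finding is a mismatch between 9.1 and 6.4.

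The size cannot be derived from the documents and may be small. It would be tempting to quote a percentage of false DR events, but any such figure rests on assumed rates alone. The conclusion depends on rule e) being applied literally and on no restriction in the adverse-event chapter. If that chapter already requires attribution to diabetic eye disease, what remains is to bring 9.1 into line with it. Correction is still worthwhile because DR is a primary outcome and the change is cheap.

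**What to change.** Amend rule e) in section 9.1 so that the following count as incident DR:

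- retinal laser photocoagulation, intravitreal anti-VEGF therapy or vitrectomy given for diabetic retinopathy or diabetic macular edema;
- vitreous/preretinal hemorrhage attributed to DR;
- CSME;
- diabetes-related blindness.

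The last two are existing components and must not be lost in the rewording. Align section 6.4 with this list.

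If it is not already recorded, record the indication with each event as DR or diabetic macular edema, other, or unknown. Exclude events with a documented non-diabetic indication. Keep events of unknown indication in the main count and run a sensitivity analysis without them. Counting unknowns only when an image shows DR would add almost nothing, since those patients are already DR cases by image, and it would drop true cases whose images are ungradable.

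The cost is one amended rule, the matching edit in 6.4 and at most one data field. Some misclassification will remain among the unknowns, and the sensitivity analysis shows how much it could matter. The change concerns how events are classified, not how patients are treated.
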